	ANNEX 1, FLOW CHART	
	ANNEX 2, MGFA CLASSIFICATION	
22	ANNEX 3, STUDY DRUG INFUSION/OBSERVATION	34
23 A	ANNEX 4, QMG	36
24	ANNEX 5. MG-QOL15	388

25	ANNEX 6, MG-ADL	399
26	ANNEX 7, EQ5D	40

1 Summary

PROTOCOL IDENTITY AND STUDY OBJECTIVE

EudraCT-number: 2015-005749-30

Protocol number 2015-00887

Protocol title: A randomized, double-blind, placebocontrolled multicenter study evaluating the

safety and efficacy of Rituximab (Mabthera®) in patients with new-onset generalized

Myasthenia gravis (MG).

Study objective To evaluate the safety and efficacy of

rituximab (Mabthera) in the treatment of

patients with recent onset MG.

STUDY DRUG

Product: Mabthera (Rituximab)

Pharmaceutical formula: Concentrate for infusion, solution

Dose 500 mg
Mode of administration: Intravenous

METODOLOGY

Study design: Randomized, double-blind, placebo-controlled

multicenter study

Primary question: Is rituximab more effective than placebo at

achieving minimal clinical MG symptoms without the need for higher doses of oral corticosteroids or rescue treatments at 16

weeks post-treatment?

Primary endpoint: Proportion of patients with QMG score ≤ 4

and a daily dose of Prednisolone of ≤ 10mg and no rescue treatment at 16 weeks after

study start

STUDY POPULATION	
Study subjects:	Patients with new onset generalized myasthenia gravis (MG)
Study size:	N=47
Inclusion criteria	1. Patients with oculobulbar, bulbar or generalized MG ≥ 18 years of age and ≤ 12 months after onset of generalized symptoms or neurophysiological detection of generalized disease. 2. The diagnosis of MG should be made by the following tests: Clinical neurological status with motor symptoms compatible with MG and ≥ 2 of the following: a Positive serological test for antiacetylcholine receptor antibodies (AChR), and/or b. For MG typical findings on neurophysiological testing of neuromuscular

Protocoll nr: 2015-00887 Date: 2021-04-26 Version 7.0 (ENG)

transmission by single fiber electromyography (SFEMG) and / or repetitive nerve stimulation (RNS),

and/or

- c. Positive anticholinesterase test, e.g. edrophonium chloride test or improvement of MG symptoms with oral cholinesterase inhibitors at the discretion of the treating physician.
- 3. MGFA clinical classification class II to IV at screening.
- 4. Quantitative MG score ≥ 6 at screening
- 5. Women of childbearing potential must have a negative pregnancy test.
- 6. Patients must have given written informed consent.
- 7. Patients must be able and willing to follow all study procedures.

Exclusion criteria

Weakness affecting only ocular or periocular muscles (MGFA class I).

- 2. MG crisis at screening (MGFA class V)
- 3. Thymectomy already performed. To avoid difficulties in evaluating the effect of the study drug, thymectomy, in cases where it is deemed indicated, should be planned for the follow-up period, i.e. only after the first 24 weeks.
- 4. Strong suspicion of thymoma and where thymectomy according to the treating physician should be performed within 24 weeks.
- 5. Active cancer, unless adequately treated
- 6. Pregnancy or breast-feeding.
- 7. Any ongoing acute or chronic viral or systemic bacterial infection including HIV and latent hepatitis B, which is clinically significant in the opinion of the study physician, and which has not been treated with appropriate antibiotic / antiviral drugs.
- 8. Severe heart failure (New York Heart Association Class IV) or severe uncontrolled heart disease
- 9. Previous use of immunosuppressive drugs including rituximab, azathioprine, ciclosporin and MMF. The use of Prednisolone at a dose of ≤40mg / d within 3 months and IVIG and PLEX 12 months from the screening date does not constitute an exclusion criterion. Note that this does not apply to treatment with immunosuppressive drugs / corticosteroids (excluding rituximab) for indications other than MG, provided that> 12 months have elapsed since the end of treatment.
- 10. Hypersensitivity to the active substance, to murine proteins or to any of the other excipients in the study medicinal product11. Participation in any other clinical drug
- study or exposure to any other study drug,

study product or study procedures within 30 days before screening.

12. Any medical condition which, in the opinion of the study physician, may interfere with the patient's participation in the study, poses any additional risk to the patient, or which complicates the assessment of the patients.

13. Vaccination within 4 weeks before inclusion

TIDSPLAN

Study period: Q4 2016 – Q1 2021

Recruitment period: Q4 2016 – Q1 2020

Protocoll nr: 2015-00887

Date: 2021-04-26

Version 7.0 (ENG)

2 Abbreviations

Förkortning	Förklaring
AE	Adverse Event
APL	Apotek Produktion & Laboratorier AB
CMM	Center for Molecular Medicine
DSUR	Development Safety Update Report
EQ5D	EuroQol 5-dimensions
GCP	Good Clinical Practice
ICH	International Conference on Harmonisation
IV	Intravenous
IVIG	Intravenous immunoglobulines
KI	Karolinska Institutet
MG	Myasthenia gravis
MGFA	Myasthenia Gravis Foundation of America
MG-QOL 15	Quality of life - myasthenia gravis
MMF	Mycophenolate mofetil (Cellcept)
RNS	Repetitive nerve stimulation
SAE	Serious Adverse Event
SUSAR	Suspected Unexpected Serious Adverse Event
QMG	Quantitative Myasthenia Gravis scale

3 Administrative information

5.1 Background and rationale

Myasthenia gravis (MG) is a relatively rare autoimmune disease of the neuromuscular junction, caused by a defective neuromuscular transmission, which results from autoantibodies that bind to proteins involved in signaling at the neuromuscular synapse. MG is characterized by weakness and fatigue in skeletal muscles and occurs at all ages, but mainly among young adult women and in people of both sexes over 60 years. About 2,500 people in Sweden have the disease according to a recent epidemiological study¹.

The disease has a large variation in severity, where in more severe cases you need intensive care for a shorter or longer periods of time. Traditionally, MG is treated with purely symptom-relieving drugs and immunomodulatory / suppressive drugs. Pure symptom-relieving cholinesterase inhibitors can be sufficient in milder cases, but immunosuppressive agents must often be used to avoid persistent symptoms, which can be life-threatening as a result of failing respiratory functions.

MG is traditionally treated with high doses of corticosteroids (Prednisolone up to 60 mg / day) over a longer periods of time, which carries significant risks of side effects. Since the 1970s, therefore, oral immunosuppressive drugs have also been used as corticosteroid-sparing agents. This group includes azathioprine (Imurel), cyclosporine (Sandimmun) and mycophenolate (Cellcept). None of these drugs have the indication MG and the onset of effect is usually delayed.

In the largest randomized study to date in MG, in which 176 patients with persistent symptoms were randomized 1: 1 to mycophenolate or placebo, the active arm showed no significant improvement over placebo over 6 months on the primary endpoint; the proportion of patients with minimal symptoms and a daily dose of prednisolone \leq 10 mg per day (44% in active arm versus 39% in placebo)². In another study, 80 patients with mild to moderate generalized AChR-positive MG and a daily dose of 20 mg Prednisolone were randomized to MMF and placebo, respectively, and followed for 12 weeks with MMF. The primary efficacy parameter was change in the quantitative MG (QMG) scale³, which did not differ significantly between the study arms (p = 0.71)⁴. These study results show that a significant proportion of MG patients continue to have generalized weakness involving limb weakness and bulbar symptoms (difficulty chewing, swallowing, speaking, and breathing) despite adequate dosing of immunosuppressive therapy. There is thus a great need to test newer treatment algorithms, which may include more effective biological drugs.

Several minor observational studies have shown that rituximab, an anti-CD20 monoclonal antibody that eliminates B cells, may have beneficial effects in treatment-refractory MG. There are currently a couple of randomized drug trials with rituximab using a haematological treatment protocol with repeated dosing of the drug for several weeks, with a total dose of over 2,000 mg. At Karolinska University Hospital, in recent years, more than 30 patients with MG, both refractory and new-onset patients, have been treated with rituximab, with a single infusion of 500 mg with good results and without serious side effects. In some cases, the treatment has been repeated after 6-12 months. An interesting observation is that the effect of the treatment seems to come much earlier than traditional immunosuppressive drugs, which leads to a reduced risk of hospitalizations and exposure to unnecessarily high cortisone doses. These experiences warrant further investigation of the efficacy and safety of rituximab in newly-diagnosed MG patients with moderate-to-severe disease and a low-dose protocol. The same dose (500 mg) is used by us for multiple sclerosis, where we currently have about 500 patients under treatment at Karolinska University Hospital.

The aim of the current study is to study the effect of rituximab compared to placebo in the treatment of newly debuted MG of at least moderate severity and with a risk of deterioration, i.e. subjects for whom prednisolone administration, repeated doses of IVIG or the addition of immunosuppressive medication may be indicated.

Protocoll nr: 2015-00887 Date: 2021-04-26 Version 7.0 (ENG)

on 7.0 (ENG) 13(42)

6 Study questions

6.1 Primary question

Is rituximab more effective than placebo at achieving minimal clinical MG symptoms without the need for higher doses of oral corticosteroids or rescue treatments at 16 weeks post-treatment?

6.2 Secondary questions

Is rituximab more effective than placebo at achieving improvement in standardized muscle fatigue testing at 24 weeks post-treatment?

Is rituximab more effective than placebo at achieving an improvement in the ability to perform activities of daily living at 16 weeks after treatment?

Is rituximab more effective than placebo at achieving an improvement in perceived quality of life at 16 weeks post-treatment?

6.3 Tertiary and explorative questions

Is rituximab more effective than placebo at achieving improvement in standardized muscular fatigue tests at 16, 36 and 48 weeks after treatment?

Is rituximab more effective than placebo at achieving differences in the ability to perform activities of daily living at 24, 36 and 48 weeks after treatment?

Is rituximab more effective than placebo at achieving an improvement in perceived quality of life at 24, 36 and 48 weeks after treatment?

Is rituximab more effective than placebo at achieving normalization of repetitive nerve stimulation at 24 weeks post-treatment?

To study the safety and effect of rituximab on the need for care in the treatment of MG

To study drug antibodies and immunological markers 6 months after treatment

7 Endpoints

7.1 Primary endpoint

Proportion of patients with QMG score \leq 4 and a daily dose of Prednisolone of \leq 10mg and no rescue treatment at 16 weeks after study start

7.2 Secondary endpoints

QMG scores at 24 weeks after treatment

MG-ADL scores at 16 weeks after treatment

MG-QOL scores at 16 weeks after treatment

7.3 Tertiary and explorative endpoints

Proportion of patients with QMG score ≤ 4 and a daily prednisolone dose ≤ 10mg and no rescue treatment at 24 weeks after treatment

QMG scores at 16, 36 and 48 weeks after treatment

MG-ADL scores at 24, 36 and 48 weeks after treatment

EQ5D scores at 16, 24, 36 and 48 weeks after treatment

MG-QOL scores at 24, 36 and 48 weeks after treatment

Hospital admissions

Rescue treatments

Adverse events

Autoantibody levels 24 weeks after treatment

Blood samples for exploratory immunological analyses at baseline, 16 and 24 weeks after treatment

Protocoll nr: 2015-00887 Date: 2021-04-26

Version 7.0 (ENG) 14(42)

8 Design

8.1 Study design

The study is a randomized, double-blind, parallel group, placebo-controlled multicenter study aimed at evaluating the safety and efficacy of rituximab (Mabthera) in the treatment of patients with new-onset MG. The study is expected to be carried out at 10 -15 centers in Sweden. In the study, approximately 50 individuals will be randomized 1: 1 to one of two treatment arms, (1) rituximab or (2) placebo infusion (NaCl).

Possible study participants are informed orally and in writing about the study during in- or outpatient care at the respective neurology clinic and can, after signed consent, be included in the study. *No study-related measures can be carried out before the consent is signed.*

8.2 Screening period

If the patient agrees to participate in the study, the following examinations are performed:

- Review of medical history and current medication
- Somatic status: including general condition (blood pressure, heart rate, body temperature), age, sex, height, weight and disease activity.
- Evaluation of muscle strength, QMG. If the patient has <6 in QMG, the evaluation must be repeated after at least 6 hours since last dose of cholinesterase inhibitors

Repetitive neurophysiology, RNS, for study subjects with a neurophysiology clinic in the hospital. See section 11.6, Neurophysiology

- Questionnaire regarding quality of life, EQ5D and MG-QoL15
- Ability to perform daily activities, MG-ADL.
- Blood tests: CBC incl. differential, Na, K, Creatinine, Asat, Alat, CRP, Glucose, hepatitis B screening, total IgG.
- Pregnancy test if the patient is a woman of childbearing age.

All women of childbearing potential are instructed to use effective contraception throughout the study after receiving the study drug. One of the following counts as an effective contraceptive:

- * Combined hormonal contraceptives (estrogen and progestin) that inhibit ovulation
- -oral, intravaginal, or transdermal
- * Progesterone -hormonal contraceptives that inhibit ovulation
- -oral, injectable, or implantable
- * Spiral
- * Bilateral fallopian tube occlusion
- * Vasectomized partner
- * Sexual abstinence, to refrain from heterosexual intercourse throughout the study.

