8.4 Study drug administration, baseline (V.0)

Study drug administration is carried out at a ward or outpatient clinic, depending on whether the patient is hospitalized or policlinic.

Inclusion and exclusion criteria are reconciled and QMG, MG-ADL, MG-QOL15, EQ5D are performed and somatic status is checked.

Note that QMG testing should be performed ≥12 hours after last dose of cholinesterase inhibitors.

To reduce the risk of allergic reactions, 1,000 mg paracetamol (Alvedon), 50 mg prednisone (Deltison) and 10 mg Cetirizine are administered at least 45 minutes before the infusion. Blood pressure, pulse and temp are checked before starting the infusion.

Important: Before starting the infusion, take a serum tube for exploratory immunological analysis.

The blood sample is sent to the sample management Karolinska University Hospital Solna, attach study-specific consultant referral.

Study drug is administered as an intravenous infusion (2 mg rituximab / ml, total 500 mg or placebo) with increasing infusion rate for a total of about 150 minutes by the nurse in charge of the infusion with the physician in charge of the infusion as support. See Appendix 3, Mabthera Infusion Monitoring.

Speed of Infusion

0-30 min	50ml/h
30-60	100ml/h
60-90 min	150ml/h
90 min -	200ml/h

In case of allergic reactions, the infusion is stopped temporarily and if necessary, 0.5 - 1 mg clemastine (Tavegyl) iv and / or 100 mg hydrocortisone (Solu-Cortef) can be administered intravenously. If the symptoms subside, the infusion can be restarted at the initial drip rate. In case of more severe reactions affecting systemic condition or with circulatory effects, the infusion should be stopped permanently.

The patient is monitored throughout the infusion and blood pressure, pulse and temperature are checked again after the end of the administration. The patient is then observed for another 60 minutes.

Important: before returning home, make sure the patient has:

- Current contact information
- Informed to contact new / aggravated symptoms urgently, no later than 48 hours.
- Received instructions on medication with Prednisolone schedule if it has been deemed indicated

The prednisolone schedule listed below may, if Prednisolone has not already been started on a purely clinical indication, be initiated immediately after the screening visit, or alternatively the day after administration of study drugs, if cortisone treatment is judged clinically indicated by the treating physician:

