9.1 Inclusion criteria

- 1. Patients with oculobulbar, bulbar or generalized MG \geq 18 years of age and \leq 12 months after onset of generalized symptoms or neurophysiological detection of generalized disease.
- 2. The diagnosis of MG should be made by the following tests: Clinical neurological status with motor symptoms compatible with MG and ≥ 2 of the following:
 - a Positive serological test for anti-acetylcholine receptor antibodies (AChR),

and/or

b. For MG typical findings on neuro-physiological testing of neuromuscular transmission by single fiber electromyography (SFEMG) and / or repetitive nerve stimulation (RNS),

and/or

- c. Positive anticholinesterase test, e.g. edrophonium chloride test or improvement of MG symptoms with oral cholinesterase inhibitors at the discretion of the treating physician.
- 3. MGFA clinical classification class II to IV at screening.
- 4. Quantitative MG score ≥ 6 at screening
- 5. Women of childbearing potential must have a negative pregnancy test.
- 6. Patients must have given written informed consent.
- 7. Patients must be able and willing to follow all study procedures.

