9.2 Exclusion criteria

- 1. Weakness affecting only ocular or periocular muscles (MGFA class I).
- 2. MG crisis at screening (MGFA class V).
- 3. Thymectomy already performed. To avoid difficulties in evaluating the effect of the study drug, thymectomy, in cases where it is deemed indicated, should be planned for the follow-up period, i.e. only after the first 24 weeks.
- 4. Strong suspicion of thymoma and where thymectomy according to the treating physician should be performed within 24 weeks.
- 5. Activecancer, unless adequately treated.
- 6. Pregnancy or breast-feeding.
- 7. Any ongoing acute or chronic viral or systemic bacterial infection including HIV, latent hepatitis B, which is clinically significant in the opinion of the study physician, and which has not been treated with appropriate antibiotic / antiviral drugs.
- 8. Severe heart failure (New York Heart Association Class IV) or severe uncontrolled heart disease
- 9. Previous use of immunosuppressive drugs including rituximab, azathioprine, ciclosporin and MMF. The use of Prednisolone at a dose of ≤40mg / d within 3 months and IVIG and PLEX 12 months from the screening date does not constitute an exclusion criterion. Please also note that this does not apply to treatment with immunosuppressive drugs / corticosteroids (excluding rituximab) for indications other than MG, provided that > 12 months have elapsed since the end of treatment.
- 10. Hypersensitivity to the active substance, to murine proteins or to any of the other excipients in the study medicinal product
- 11. Participation in any other clinical drug study or exposure to any other study drug, study product or study procedures within 30 days before screening.
- 12. Any medical condition which, in the opinion of the study physician, may interfere with the patient's participation in the study, poses any additional risk to the patient, or which complicates the assessment of the patients.

Protocoll nr: 2015-00887 Date: 2021-04-26

Version 7.0 (ENG) 19(42)

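### Pregnancy is tested only at screening, the time to infusion is not limited, and contraception is worded as starting after dosing, so an early unrecognised pregnancy could be missed

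*Combined protocol and SAP*

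**What the plan says.** **Eligibility.** Exclusion criterion 6 in section 9.2 is "Pregnancy or breast-feeding". Inclusion criterion 5 in section 9.1 is "Women of childbearing potential must have a negative pregnancy test", with no timing attached. By contrast, criterion 3 reads "MGFA clinical classification class II to IV at screening", and criterion 4 is tied to screening in the same way.

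**Testing.** Section 8.2 lists, among the screening examinations, "Pregnancy test if the patient is a woman of childbearing age". In Annex 1 the pregnancy test row is marked only in the screening column.

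**Baseline visit.** Section 8.4 says "Inclusion and exclusion criteria are reconciled and QMG, MG-ADL, MG-QOL15, EQ5D are performed and somatic status is checked". It lists no pregnancy test.

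**Contraception.** Section 8.2 says "All women of childbearing potential are instructed to use effective contraception throughout the study after receiving the study drug".

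**Interval.** Section 8.3 leaves the infusion date to be agreed with the patient once the criteria are met. No section gives a maximum time from screening to infusion.

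**The concern.** The trial gives one infusion, which cannot be taken back. The protocol excludes pregnant women, but its only scheduled test is done at an earlier visit, an unstated time before dosing. On the wording, no contraception is required in between. Women of childbearing potential are expected: adults from 18 are eligible, and section 5.1 names young adult women as one of the main groups with the disease.

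What is at stake is avoidable fetal exposure, not a demonstrated toxic effect. Section 10.2 reports dose-dependent low B-cell levels in the monkey fetus and reduced IgG in the affected newborns. It also reports no evidence of fetal toxicity at doses up to 100 mg/kg, B-cell recovery within 6 months of birth and no effect on the response to vaccination. The animals were treated on gestational days 20 to 50, so these data do not directly describe earlier exposure, which is the kind this gap would allow.

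**Working it through.** No figure in the plan bears on this point and no arithmetic applies. The check sets the relevant sections side by side and asks whether any scheduled step would detect or prevent a pregnancy beginning between screening and V.0.

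1. **Is there a second test?** No. Section 8.4 itemises the V.0 procedures without one. Annex 1 repeats the physical examination, MGFA class, QMG and the questionnaires at baseline but leaves the pregnancy row blank there. The only baseline blood entry carries footnote 8, the serum tube taken before dosing. Section 8.4 describes that tube as exploratory and says of it "The blood sample is sent to the sample management Karolinska University Hospital Solna, attach study-specific consultant referral". It gives the site no result before the infusion.

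2. **Does the V.0 eligibility check imply a fresh test?** It may, but it does not have to. Criterion 5 is not tied to screening, so a site could read the recheck as calling for a current result. It also sets no age for the result, so a site could confirm it from the screening test and be fully compliant.

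3. **Does the pre-dose withdrawal rule help?** Section 9.3 lets the investigator stop a patient before dosing if new information shows the criteria are no longer met. No scheduled procedure would produce that information for an unrecognised pregnancy.

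4. **Is the interval short by design?** The text does not settle it.
   - *Pointing to short:* Annex 1 puts randomisation in the screening column.
   - *Pointing to separate occasions:* section 8.3 describes a sequence of criteria met, patient contacted, date agreed, then the pharmacy contacted for randomisation and ordering. Section 8.4 allows prednisolone to "be initiated immediately after the screening visit, or alternatively the day after administration of study drugs". Section 10.7 has its own phase between screening and randomisation, in which plasma exchange is permitted. The only plasma exchange regimen in the protocol, the rescue regimen in section 10.8, runs 10 to 14 days, so an interval of that order is compatible with the text.
   - *Not relevant:* the 36-hour shelf life in section 10.4 runs from preparation of the bag, not from the pregnancy test.

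5. **Is contraception required in the gap?** Not by the wording of section 8.2, which speaks of the period after study drug.

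**Result.** A known or suspected pregnancy should be caught. For an unrecognised one conceived after the screening test, no scheduled step is designed to find it and no visible rule makes it less likely.

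**The case against.** The strongest reply is that the protocol already handles most of this. Pregnancy excludes, the criteria are rechecked immediately before dosing, and the investigator may stop. A careful site would test again or ask. This is right for known or suspected pregnancy. For an unrecognised one it relies on each of 10 to 15 centres choosing the stricter reading of criterion 5.

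A second reply is that the interval was probably short. Annex 1 suggests so. The prednisolone schedule, which may begin after screening yet is described in section 10.7 as an 8-week taper from randomisation, fits best with a small gap. If the gap is a few days, a V.0 test adds little, because a very recent conception cannot be detected. That stands as a limit on the test. It does not weaken the case for starting contraception at screening, which is the part that works over a short gap.

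A third is that the contraception sentence is translated, sits in the screening section and lists methods that must already be in place, so it may only have been meant to set duration. That reading is possible, but the words do not say it. The consent pages are not available, so advice given to patients there cannot be judged.

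Other limits also stand. The trial is small (N=47 in the Summary), and about half of any women affected would receive saline. This version is dated 2021-04-26, after the stated recruitment period of Q4 2016 to Q1 2020.

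**Conclusion.** The concern holds. The plan schedules one pregnancy test, sets no maximum time from it to the infusion, and words contraception as beginning after dosing. A site following the text exactly could give rituximab to a woman with an unrecognised early pregnancy.

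The size cannot be estimated, and no figure is offered. The conclusion rests on the visible text only and assumes that the removed pages do not close the gap. Confidence is moderate, because the real interval and site practice are unknown. The change is worth making because it is cheap and the dose is irreversible, not because harm has been shown. On the stated dates, its practical use is for later enrolment or for reuse of the protocol.

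**What to change.** 1. In section 8.2, require effective contraception from screening, through the infusion and for the rest of the study. This costs wording only and is worth doing on its own.
2. In section 8.4, inclusion criterion 5 and Annex 1, require a negative pregnancy test at V.0 for women of childbearing potential, for example a urine test read on site, before premedication and infusion. Waive it if the screening test falls within a short window set by the sponsor, and state that window.

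No test can exclude a conception too recent to detect. The first change makes that less likely.

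**Cost.** One simple test at an existing visit. The exploratory serum tube cannot serve for it. V.0 already includes QMG, about 20 to 30 minutes by section 11.2, and at least 45 minutes from premedication to infusion by section 8.4. The test should fit, assuming its result is available during QMG. Rarely, a positive result would waste a prepared bag and leave a randomised, undosed patient. Section 9.3 allows that patient to be replaced, but section 13.2 specifies an intention-to-treat analysis without saying how she would be counted. One sentence there would settle it. The effect on power and on the primary analysis would be negligible.
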